Structural Types of the Foot and Their Influence on Core and Sports Performance in College
Athletes

NCT ID not yet assigned

Date: 25/August/2022

Structural Types of the Foot and Their Influence on Core and Sports Performance in College Athletes

General Objective:

The objective of this study is to assess the impact of foot arch height and the implementation of a corrective exercise program on foot posture alterations in college athletes. The evaluation will focus on three aspects: postural stability, muscular activity at the center of gravity, and sports performance. This assessment will be conducted using advanced measurement systems such as Surface Electromyography, motion analysis technology, Ergospirometry, and body motion kinematics measurement systems. The findings of this study aim to contribute to the optimization of athlete training and overall performance.

Specific Objectives:

1. Compare the average muscular activity at the center of gravity and both static and dynamic stability among college athletes with low, high, and neutral foot arches. This analysis will employ Surface Electromyography and a 3D motion measurement system. The goal is to determine the potential influence of different foot structural types on core muscle activity and overall stability in athletes.
2. Assess the potential variations in jump force, acceleration, step speed, race time, maximum oxygen consumption, and anaerobic threshold among college athletes with high, low, or neutral foot arches. This investigation will utilize biomechanical analysis technology and Ergospirometry, with the aim of identifying any possible impact of varying foot structural types on athletes' performance capacity.
3. Evaluate the potential changes in terms of center of gravity muscle activity and both static and dynamic stability after a 12-week exercise program designed to correct different foot structural types (high or low) in college athletes. This assessment will employ Surface Electromyography and a 3D motion measurement system, with the objective of establishing the effectiveness of these exercises in improving athletes' body stability.
4. Determine the potential alterations in VO₂max, anaerobic threshold, jump force, acceleration, step speed, and race time in college athletes, following a 12-week exercise program aimed at correcting two foot structural types (high or low). This investigation will use Ergospirometry and a 3D motion kinematics assessment system to evaluate possible improvements in sports performance resulting from the exercise program.

Methodology:

Design and Sample: An observational study design was employed to assess the impact of foot structural types on postural stability, activity of core stabilizing muscles, maximum oxygen consumption (VO₂max), anaerobic threshold, and lower limb performance in male college athletes over 18 years old from the University of Magdalena, participating in various sports modalities such as rugby, soccer, basketball, volleyball, tennis, table tennis, karate, and cheerleading. For evaluating the effects of a corrective exercise program targeting high or low foot posture alterations on the same variables, an experimental design was used. Stratified random sampling was employed for convenience, and 35 participants with low medial arch, 32 with high arch, and 36 with neutral arch were selected for the observational studies. For the experimental studies, 33, 31, and 33 participants were selected, respectively, from a pool of 230 candidate athletes. G Power 3.1.9.7 software was used to determine the appropriate sample size, considering three independent groups, an alpha level set at 0.05, a power (1-β) of 0.80, and an effect size (f) of 0.40.

Foot Type Evaluation: The Foot Arch Index, which determines the medial arch height by measuring the ratio between the midfoot area and the total foot area (excluding toes), was used to evaluate the foot type. An index less than 0.21 indicated a high-arched foot, an index greater than 0.26 indicated a flat foot, and an index between 0.21 and 0.26 was considered a "neutral" arch. Participants' footprints were obtained using a washable ink pad, and analysis software was used to calculate the Foot Arch Index.

Study Instruments: State-of-the-art equipment was used, including 3D inertial sensors for assessing static and dynamic postural stability (optogate and Gyko, Microgate® Bolzano, Italy), surface electromyography to measure neuromuscular activity of core muscles (Biomec® Newport, United Kingdom), ergospirometry equipment to measure oxygen consumption and anaerobic threshold (Cosmed® K5, Rome, Italy), motion analysis equipment to assess jump power and speed (Gyko, Microgate® Bolzano, Italy), and photocell sensors to measure running speed and times (Witty-Microgate® Bolzano, Italy). Anthropometric measurements were conducted using a bioimpedance equipment (InBody® 970, Seoul, Korea).

Measurement of Dependent Variables: This study evaluated the action of core muscles and static and dynamic body stability. Surface electromyography (sEMG) was used to measure muscle activity during functional exercises, such as unstable Bulgarian squats with weights for Rectus Abdominis (RA), front plank with shoulder adduction and posterior pelvic tilt for Internal Oblique (IO), standing unilateral dumbbell press for External Oblique (EO), and deadlift for Spinal Erectors (SE). These postures demonstrated the highest activity in electromyography studies. Core assessment exercises were performed with each muscle group holding an isometric contraction for 5 seconds. Parameters recommended in the literature were used for electrode placement on RA and for SE, IO, and EO. Static postural control tests were conducted with eyes closed to increase changes in somatosensory and muscular components of the postural control system. Athletes remained motionless for 10 seconds with closed eyes, and four measurements were taken for the dominant foot, with 30-second rests between each measurement.

Different parameters such as average distance and speed, anteroposterior distance and speed, mediolateral distance and speed, and covered area were measured. Dynamic postural control was evaluated by performing five single-leg jumps with the dominant foot to obtain data on average

power and average displacement to the left/right and forward/backward, as well as covered area. All muscle strength measurements and assessments of static and dynamic postural control were conducted on different days to avoid muscle fatigue.

The measurements were performed during the general preparation stage of each sports semester, with no changes in diet and approximately two hours after the main meal of the day. To evaluate aerobic capacity (VO₂max) and anaerobic threshold, participants underwent an incremental treadmill test. The test began with a 3-minute warm-up at a speed of 4.8 km/h, increasing 1.2 km/h every minute while maintaining a constant 3% incline. Then, the main test started at 8.2 km/h with a constant 3% incline, and speed increased by 1.2 km/h every two minutes until exhaustion. The V-Slope method was used to measure VO₂ values at the anaerobic threshold. VO₂max was estimated based on three criteria: when the participant could not continue the test, when the VCO₂/VO₂ ratio exceeded 1.1, or when the maximum heart rate was reached with no more than a 10 beats/minute difference. To measure performance capacity, the countermovement jump (CMJ) technique was used, which involved jumping from a kneeling and hip-flexed position. Different parameters, such as maximum force, maximum velocity, maximum power, and level of developed force, were recorded. To assess lower limb speed and acceleration, the 40-meter linear acceleration test was employed, which demonstrated good reliability and validity.

Program of Corrective Foot Posture Exercises: In the experimental studies, the intervention group followed a 12-week exercise program aimed at correcting foot posture alterations, while the control group performed flexibility exercises. The exercises for the intervention group varied based on foot structural type (high or low) and focused on strengthening intrinsic and extrinsic foot muscles. The program was conducted under the supervision of an experienced physiotherapist. For participants with flat feet, exercises focused on strengthening the abductor hallucis, flexor digitorum brevis, and quadratus plantae muscles, with a progressive load over eight weeks. Additionally, myofascial release of the lateral long fibular muscle was performed. For participants with high arches, exercises emphasized improving flexibility of the tibialis posterior and gastrosoleus muscles. Strengthening exercises for the same muscles as in the flat feet group were also performed, with a gradual increase in load.

Statistical Analysis: Data were reported as mean \pm standard deviation and analyzed using IBM SPSS Statistics (version 21, IBM Corp., NY, USA). The normality of each variable for different foot types (low, high, or neutral) was checked using the Shapiro-Wilk test. The significance of variables such as age, weight, height, and muscle/fat percentages among the three foot types was evaluated using ANOVA if the variables followed a normal distribution, or the Kruskal-Wallis test if they did not. For descriptive studies, ANOVA was used for normally distributed dependent variables or Kruskal-Wallis for non-normally distributed variables. Levene's test was used to assess homogeneity of variances. Post-hoc analysis with Bonferroni correction was performed to determine differences between groups. Pearson's or Spearman's correlation was used to assess the relationship between variables. For experimental studies, the effects of exercise on dependent variables were assessed using repeated-measures ANOVA or Friedman's test. Levene's test was used for variance homogeneity. Post-hoc analysis with Tukey correction was conducted to assess pre-post exercise significances of dependent variables. Eta-squared (η^2_p) or Kendall's W concordance coefficient was used to evaluate the effect size of the exercise program on foot types. The significance level for both studies was set at $p \leq 0.05$.

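### The plan does not state the controls' foot type or any allocation to arm, and names no between-arm analysis, so the causal parts of Objectives 3 and 4 are not supported

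*Combined protocol and SAP*

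**What the plan says.** **Arms.** Methodology, Program of Corrective Foot Posture Exercises, states that "the intervention group followed a 12-week exercise program aimed at correcting foot posture alterations, while the control group performed flexibility exercises". Content for the corrective program is then set out for flat feet and for high arches. There is no version for neutral arches, and the controls' foot type is not given.

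**Sample.** Methodology, Design and Sample, counts athletes by foot type only, in the order low, high, neutral: "For the experimental studies, 33, 31, and 33 participants were selected, respectively, from a pool of 230 candidate athletes". The sample size was computed "considering three independent groups", with "an alpha level set at 0.05, a power (1-β) of 0.80, and an effect size (f) of 0.40". No arm sizes, allocation ratio or method of allocation appear. Randomness is mentioned only for drawing participants from the pool (stratified random sampling, for convenience), which is not assignment to treatment.

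**Analysis.** Statistical Analysis plans repeated-measures ANOVA or Friedman's test for the experimental studies, Tukey-corrected pre-post tests, and an effect size described by foot type. It names no program-versus-control contrast and no arm-by-time term.

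**Aims.** Specific Objective 3 asks for changes after the program in high or low arches, "with the objective of establishing the effectiveness of these exercises in improving athletes' body stability". Objective 4 likewise asks for changes in performance, and for gains that result from the program. Each objective therefore has a descriptive part and a causal part.

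**The concern.** A causal claim about the program needs athletes of the same foot type who did not receive it, assigned in a way that does not itself predict the outcome. The plan does not show that such athletes exist. If the three foot-type groups are also the treatment groups, any difference in change between program and control athletes could come from the program. It could equally come from how different foot types respond to 12 weeks of training, retesting and regression to the mean. If the controls were drawn from low- and high-arch athletes by an unstated route, the comparison is open to selection. If only the pre-post tests are used, there is no comparison with controls at all.

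At stake is the conclusion of the experimental half of the study: a statement that the exercises work, resting on data that could not show it.

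**Working it through.** **1. The plan's own sample size.** Inputs from Design and Sample: three groups, alpha 0.05, power 0.80, f = 0.40. For one-way ANOVA the noncentrality is λ = f²N, with 2 and N − 3 degrees of freedom.

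- N = 63: λ = 0.16 × 63 = 10.08, power 0.798.
- N = 66 (22 per group): λ = 0.16 × 66 = 10.56, power 0.818. This is the minimum with equal groups.
- N = 33 + 31 + 33 = 97: λ = 15.52, power 0.944.

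The plan does not state the N that its inputs gave. The 97 selected exceeds 66, so numbers are not short for a three-group comparison. That calculation compares foot types. It contains no program-versus-control contrast.

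**2. Who can be a control.** There are two readings.

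- *Neutral athletes are the control.* Neutral is the only experimental group without corrective content, and three groups appear in both the sample and the power calculation. Of the 33 + 31 = 64 low- and high-arch athletes, none is then a control. For the low arch, the observed difference in change is

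  (low, program − low, flexibility) + (low, flexibility − neutral, flexibility).

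  The first bracket is the program effect. The second is a foot-type difference. With no low-arch athlete doing flexibility exercises, the two cannot be separated by any analysis. The same holds for the high arch.
- *Some low- or high-arch athletes are controls.* The first bracket could then be estimated, but no random allocation is stated and the number in each arm is unknown. The 33 neutral athletes would have no stated role in the experimental studies.

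**3. Illustration under the first reading.** Suppose the program does nothing and untreated 12-week change differs between foot types by δ SD. For a two-sided t test at 0.05 with 33 v 33, the noncentrality is δ√(33 × 33/66) = 4.062δ, with 64 df.

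| δ (assumed) | Noncentrality | Rejection rate |
|---|---|---|
| 0.2 | 0.81 | 0.126 |
| 0.3 | 1.22 | 0.225 |
| 0.5 | 2.03 | 0.516 |

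The nominal rate is 0.05. For high v neutral (31 v 33) the rates are 0.123, 0.219 and 0.503. The documents give no value of δ and do not name this test, so these figures show sensitivity only.

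**4. What the same athletes would give if randomised within foot type.** Assumptions: 1:1 allocation, two-sided alpha 0.05, and d = 2f = 0.80 in SDs of change. The conversion d = 2f holds for two equal groups; the plan set f for three groups and gives no effect size for this contrast. Noncentrality is d√(n₁n₂/(n₁ + n₂)).

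| Comparison | n₁ v n₂ | Noncentrality | Power |
|---|---|---|---|
| Low and high combined | 32 v 32 | 0.8 × 4.000 = 3.20 | 0.883 |
| Low only | 17 v 16 | 0.8 × 2.871 = 2.30 | 0.605 |
| High only | 16 v 15 | 0.8 × 2.782 = 2.23 | 0.576 |

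Power 0.80 within one foot type needs 26 per arm (0.8075), that is 52 athletes of that type, against 33 and 31 selected. If the true difference were d = 0.50, combined power would be 0.504.

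**The case against.** The strongest reply is that the documents never say the neutral group is the control, so confounding with foot type is inferred, and that much of Objectives 3 and 4 can be met as written. Both points stand. Low- and high-arch controls are not excluded. The objectives ask first for changes after the program in high or low feet, and the planned repeated-measures and pre-post tests can estimate those. A reader might infer that the two objectives cannot be answered at all; the text does not support that.

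Three further inferences also go too far.

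- *That neutral athletes must change differently because Objectives 1 and 2 allow foot types to differ.* Those objectives concern levels. A comparison of change is biased only if untreated change differs by foot type, which is plausible but does not follow from them.
- *That tailoring the program to foot type is itself a flaw.* Tailoring is the stated intervention, both versions strengthen the same muscles, and neither objective asks for a low-versus-high comparison of response.
- *That the plan has a 22% false-positive rate.* That figure needs an assumed difference in change and a test that Statistical Analysis does not name.

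The reply does not rescue the causal parts. On either reading the plan gives no random allocation and no between-arm contrast, so the claim of effectiveness has nothing to rest on.

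**Conclusion.** The concern holds in this form: control-group foot type and allocation to arm are unstated, no program-versus-control analysis is named, and the causal parts of Objectives 3 and 4 are therefore not supported. This is firm on both readings. Full aliasing of treatment with foot type, with 0 of 64 low- and high-arch athletes as controls, is conditional on the neutral group being the control; that is probable but not established. Descriptive pre-post change in low and high arches is unaffected.

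The illustrative rate of about 22% (13% to 52%) rests on δ = 0.3 SD (0.2 to 0.5) and a 33 v 33 test, both assumed. The 88% and 58-60% powers rest on 1:1 allocation and d = 0.80, also assumed. The point should be resolved before any statement that the program works.

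**What to change.** **If allocation is still open**

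- In Design and Sample and in Program of Corrective Foot Posture Exercises, state that low- and high-arch athletes are randomised 1:1, stratified by foot type, to the corrective program for their type or to flexibility exercises. Give the number per arm within each type and the method of allocation. State that neutral athletes are a descriptive reference and not the control.
- In Statistical Analysis, name the arm-by-time comparison (difference in change between program and flexibility athletes), stratified by foot type and combined over low and high, as the analysis of the program effect. Without this the randomised comparison would have no planned test.

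The athletes, measurements and sessions stay the same. The cost is that about half of the low- and high-arch athletes receive the program, and estimates for a single foot type are less precise. Report those as secondary.

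**If allocation has already been made by foot type or without randomisation**, which the past tense of the Methodology makes possible, state how athletes entered each arm. Reword Objectives 3 and 4 to describe pre-post change in low- and high-arch athletes, and remove the claims of effectiveness and of gains resulting from the program. This costs only wording and a weaker claim.

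### Experimental studies: the only stated normality check is on each variable by foot type, not on within-athlete changes, so an outcome can be diverted to Friedman's test, which with two occasions is a sign test with no between-group factor

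*Combined protocol and SAP*

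**What the plan says.** All of this is in the combined protocol and SAP.

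- **Normality check (Statistical Analysis).** "The normality of each variable for different foot types (low, high, or neutral) was checked using the Shapiro-Wilk test". No other normality check is described, and neither changes nor model residuals are mentioned.
- **Cross-sectional studies (Statistical Analysis).** The choice of test is tied explicitly to normality: "ANOVA was used for normally distributed dependent variables or Kruskal-Wallis for non-normally distributed variables".
- **Experimental studies (Statistical Analysis).** "the effects of exercise on dependent variables were assessed using repeated-measures ANOVA or" Friedman's test. The sentence gives no criterion for choosing. Post-hoc tests are described as pre-post. The effect size is partial eta-squared or Kendall's W.
- **Occasions and groups (Methodology, exercise program).** The program lasts 12 weeks, no interim assessment is described, and an intervention group is set against a control group doing flexibility exercises.
- **Numbers (Methodology, Design and Sample).** "For the experimental studies, 33, 31, and 33 participants were selected, respectively, from a pool of 230 candidate athletes". The order is low, high, neutral.

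**The concern.** Specific objectives 3 and 4 ask whether outcomes change over the 12-week program. With two occasions, the repeated-measures tests that answer this (time, and group by time) are tests on each athlete's post-minus-pre difference. Stable differences in level between athletes cancel. The normality assumption therefore concerns the changes, or equivalently the within-athlete residuals. The distribution of the variable within a foot type is a different quantity: it can be skewed while the changes are near normal.

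If the stated check sends such an outcome to Friedman's test, two things are lost. The size of each change is discarded. And Friedman's test has no between-group factor, so the comparison of intervention with control, or of foot types, over time disappears for that outcome. Many outcomes pass through this choice (sway distances, speeds and area, EMG of four muscles, jump measures, oxygen uptake, sprint). Some could then be reported as a mean change and others, in effect, as a share of athletes improving, with different effect-size measures, on the strength of a preliminary test.

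**Working it through.** **Inputs.** Group sizes 33, 31 and 33 and the 0.05 level come from the document. Two occasions follow from the pre-post wording. The documents give no SD, outcome distribution or pre-post correlation, and the sample-size inputs ("considering three independent groups", f = 0.40) do not fix a standardised change. I therefore assume normal changes with mean d = 0.5 SD of the changes, and take each foot-type group as the within-group n. The plan states no figure of its own on this point to reproduce.

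**Step 1: Friedman with two occasions.** Each athlete's ranks are (1,2) or (2,1). With n+ rises and n− falls, the statistic reduces to

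Q = (n+ − n−)² / (n+ + n−),

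which is the sign-test chi-square. On a simulated sample of 33, the full Friedman formula and this expression both gave 0.7576. The value did not move when every change was randomly rescaled with its sign kept.

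**Step 2: actual error rate.** Reject when Q > 3.841, that is, when |n+ − n−| > √(3.841·n).

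- n = 33: threshold 11.26. The difference must be odd, so it must be at least 13, giving n+ ≥ 23 or ≤ 10. The binomial probability at one half is 0.035.
- n = 31: threshold 10.91, so the difference must be at least 11, giving n+ ≥ 21 or ≤ 10. The probability is 0.071.

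**Step 3: power at d = 0.5.** The chance that a change is positive is Φ(0.5) = 0.691. The paired analysis uses the noncentral t with noncentrality 0.5·√n (2.87 at n=33, 2.78 at n=31).

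| n | Paired t / two-occasion ANOVA | Friedman (chi-square) | Actual Friedman size |
|---|---|---|---|
| 33 | 80% | 56% | 3.5% |
| 31 | 77% | 65% | 7.1% |

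The 65% at n=31 is helped by the inflated size; an exact sign test gives 50%. At n=33 and d = 0.3, 0.4 and 0.6, power is 38%, 61% and 92% for the paired analysis against 23%, 38% and 72% for Friedman. A signed-rank test at n=33 and d = 0.5 keeps 77%. For 80% power at d = 0.5, n is 34 for the paired analysis and about 53 for Friedman.

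**Step 4: diversion by chance with normal data.** Suppose any failing cell diverts the outcome.

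- Three cells (foot types): 1 − 0.95³ = 0.143.
- Six cells (foot type by pre and post): 1 − 0.95⁶ = 0.265 if independent; about 0.24 in simulation with correlated pre and post.

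**Step 5: diversion with non-normal levels (all distributions assumed).**

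- Lognormal athlete levels (log-SD 0.3 to 0.5) with additive normal changes: at least one of six raw cells fails Shapiro-Wilk in about 79% to 98% of outcomes. Checking the changes instead fails in about 13% to 16%.
- Multiplicative error instead: the raw changes themselves fail in at least one foot type in about 44% to 85% of outcomes.

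**The case against.** **The rule is inferred.** A reader might take it that the plan writes down a Shapiro-Wilk rule for Friedman's test. It does not. The explicit link is made for baseline characteristics and the cross-sectional studies only. Nor does the plan say whether one failing foot type moves the whole outcome or only that group. This stands, and the point is therefore that outcomes can be diverted, not that they are. It does not remove the point: no other criterion is offered, and without this one the plan has no rule for choosing between the two tests.

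**The check suits the cross-sectional analysis.** A reader might infer that Shapiro-Wilk by foot type is misplaced throughout. For one-way ANOVA, normality within each foot type is the residual assumption, so that use is sound. Even in the mixed model, the between-group main effect depends on athlete means, so the distribution of levels is not wholly irrelevant there. It is not, however, the effect of exercise.

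**High diversion rates are not established.** It is tempting to conclude that most outcomes would be sent to Friedman's test. The 79% to 98% needs skewed levels together with additive normal changes. Under multiplicative error the raw changes are often non-normal too, and a failed check on the raw variable then points the right way. The documents do not say which case applies.

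**A fixed log-scale list is not supported either.** Under the additive model, log-scale changes fail Shapiro-Wilk in about 45% to 85% of outcomes. The scale has to follow the residuals.

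**The power loss varies with n.** The gap is 24 points at n=33 and 12 at n=31. Part of that difference is the discreteness of the sign test, which also produces the unequal error rates.

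**Conclusion.** The point holds for the experimental studies, on the natural reading that the one normality check also selects the pre-post test. That check does not address the within-athlete changes on which the time and group-by-time tests rest, and the fallback is a sign test that drops the between-group comparison.

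The equivalence with the sign test, the error rates of 3.5% (n=33) and 7.1% (n=31), and the loss of the group-by-time contrast follow from the design; the error rates take the foot-type groups as the units analysed, with no tied pairs. The power figures in Step 3 rest on normal changes and an assumed mean change of 0.5 SD. The frequency of diversion is unknown; the 14% to 26% figure assumes normal data and that any failing cell diverts the outcome. A claim that outcomes are routinely misdirected would go beyond the documents.

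**What to change.** For the pre-post analysis:

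1. Remove the switch to Friedman's test based on Shapiro-Wilk applied to the variable by foot type.
2. Prespecify one parametric model per outcome that keeps the group-by-time contrast.
3. Judge its assumptions on changes or residuals, and use a log scale only where the residuals support it.
4. If residuals are clearly non-normal, add as a sensitivity analysis either a permutation or bootstrap p-value for the same contrast, or a rank test on the changes (signed-rank within group; rank-sum or Kruskal-Wallis between groups).

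The cross-sectional check can stay as it is. The cost is a change of SAP wording and a little extra analysis code, with no new athletes or measurements.

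### Arch groups drawn from at least eight sports are compared with no adjusted analysis, so confounding by sport or body composition is an uncontrolled risk of unknown size

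*Combined protocol and SAP*

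**What the plan says.** **Aim.** Specific objective 1 reads: "The goal is to determine the potential influence of different foot structural types on core muscle activity and overall stability in athletes". Objective 2 speaks of "identifying any possible impact of varying foot structural types". Design and Sample repeats the aim: "An observational study design was employed to assess the impact of foot structural types on postural stability".

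**Who is compared.** The participants are "male college athletes over 18 years old" at one university, "participating in various sports modalities such as rugby, soccer, basketball, volleyball, tennis, table tennis, karate, and cheerleading". The list names eight sports as examples, so there are at least eight. On selection: "Stratified random sampling was employed for convenience"; the strata are not named. The numbers are "35 participants with low medial arch, 32 with high arch, and 36 with neutral arch were selected for the observational studies", 103 in all.

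**Analysis.** The Statistical Analysis section states: "For descriptive studies, ANOVA was used for normally distributed dependent variables or Kruskal-Wallis for non-normally distributed variables". It adds Bonferroni post-hoc comparisons and Pearson or Spearman correlations between variables that it does not name. Age, weight, height and muscle/fat percentages are tested across the three foot types, with no stated consequence of either result. No covariate, blocking factor, regression, matching or sensitivity analysis is given, and sport appears in no analysis.

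**Design restrictions.** Besides sex, adult age and university, the Measurement of Dependent Variables section fixes the training stage (general preparation), unchanged diet and the time since the main meal.

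**The concern.** Arch type is observed, not assigned. If the mix of sports or the body composition differs between arch groups and also bears on an outcome such as VO₂max, jump force or 40-metre time, an unadjusted test can report that difference as an arch effect, or hide a real one. The restrictions remove sex and limit differences in season and feeding, but leave sport and body composition free to vary.

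The two factors are not in the same position. For sport, no planned analysis would show an imbalance. For body composition, the planned between-group test could show one, but nothing follows from it. Bonferroni correction deals with multiplicity, not confounding.

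**Working it through.** **1. The plan's own figure.** Design and Sample gives three groups, alpha 0.05, power 0.80 and f = 0.40, but not the N that resulted. With the noncentral F test, λ = N·f² and df 2 and N − 3, these inputs need N = 64 (66 with equal groups). The 103 selected give λ = 103 × 0.16 = 16.48 and power 0.957. There is room for covariates.

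**2. Sport (assumed scenarios).** The documents give no sport mix by arch group and no outcome SDs. Assume no arch effect and two classes of sport whose means differ by D within-class SDs, with class shares p in the low, neutral and high groups. Then λ = Σnᵢ(D·pᵢ − m)² / v, where m is the weighted mean of D·pᵢ and v = 1 + D² × weighted mean of p(1 − p). The test has df 2 and 100, critical value 3.087.

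Example, 70/50/30% and D = 1.0:
- m = (35 × 0.7 + 36 × 0.5 + 32 × 0.3)/103 = 0.506
- numerator = 35 × 0.194² + 36 × 0.006² + 32 × 0.206² = 2.68
- v = 1 + (35 × 0.21 + 36 × 0.25 + 32 × 0.21)/103 = 1.224
- λ = 2.19, so the null is rejected 24% of the time
- spurious low-high difference = 0.40/√1.223 = 0.36 within-arch SD

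| Share low/neutral/high | D = 0.5 | D = 1.0 |
|---|---|---|
| 50/50/50% | 5% | 5% |
| 55/50/45% | 5% | 6% |
| 60/50/40% | 6% | 9% |
| 70/50/30% | 10% | 24% |

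Simulation with 20,000 replicates per cell agrees, and Kruskal-Wallis is no safer (24% in the last cell). A sport difference as large as 1.5 SD would give 41% at 70/50/30%. Adjusting for the exact class restores about 5%. If 10, 20 or 30% of athletes are put in the wrong class, 8, 13 or 19% remain at 70/50/30% and D = 1.0.

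**3. The planned baseline test.** Take a covariate with low-high difference d SD and the neutral group midway. At d = 0.4, λ = 2.68 and the miss probability is 72%. At d = 0.6, 0.8 and 1.0 it is 43%, 17% and 4%.

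**4. Body composition (assumed scenarios).** If d = 0.4 and body composition correlates r = 0.3, 0.5 or 0.7 with the outcome, the bias is r × d = 0.12, 0.20 or 0.28 SD and false positives are 7, 10 or 16%. A model with sport, age and height leaves 7, 10 or 15% if those covariates are independent of body composition, but about 5, 6 or 8% if one of them correlates 0.7 with it. Adding mass, fat and muscle brings it to about 5%, provided they are measured without error.

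**5. Cost of adjustment.** With λ = 16.48/VIF and error df = 100 − k for k covariate df (VIF is the variance inflation from overlap with arch type, and covariates explain no outcome variance), power for k = 4 is 0.956, 0.90, 0.84 and 0.72 at VIF 1, 1.25, 1.5 and 2. With k = 12 (eight sports kept separate, age, height, mass, fat and muscle) and no overlap it is still 0.956. Overlap costs precision; the df cost almost nothing.

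**The case against.** **The study is descriptive.** The Statistical Analysis section says so, and objectives 1 and 2 begin by comparing groups and assessing variations. Unadjusted comparison answers that question. This stands as far as description goes; the gap arises because the same objectives and Design and Sample go on to influence and impact. Softer wording is a legitimate part of the remedy.

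**Design already gives some control.** The restrictions are real. Sampling is also called stratified, and if the strata were sports there might be some balance. They are not named, so balance can be neither assumed nor excluded.

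**Body composition is checked.** This stands in part. A reader might infer that nothing in the plan would reveal an imbalance. That is true of sport only: the baseline test would usually show body-composition differences of 0.8 SD or more. It is weak for smaller ones and leads to no action.

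**The harm is hypothetical.** This stands. A reader might take the 24% as evidence of bias. It needs a steep sport gradient and a large sport difference, both assumed; near balance the rate is 5 to 6%.

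**Adjustment can do damage.** This also stands. If arch type affects body composition or choice of sport, adjusting removes part of the effect sought, and body composition may itself alter the footprint index. That is why the unadjusted result should stay. A reader might go further and bar any conclusion unless both analyses agree. That is too strict: disagreement may mean that adjustment has corrected real confounding, and agreement does not exclude unmeasured confounders.

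**Conclusion.** The omission is certain from the text: no adjusted outcome analysis, sport in no analysis, and measured covariates that are tested but not used. Confounding by sport or body composition is a risk that the plan does not control. Its size cannot be calculated from the documents, and they do not show that it occurred. For sport differences up to 1.0 SD, the false-positive rate under the assumed mixes runs from about 5% to about 24%. The change should be made because the aim is stated as influence and the remedy is cheap.

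**What to change.** Keep the planned unadjusted test and report beside it, for each outcome:

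1. a linear model of foot type with sport, age and height. Fix the sport categories without looking at outcomes, and collapse them only where sports are sparse;
2. the same model plus body mass and fat and muscle percentage.

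Give Bonferroni-adjusted contrasts of adjusted means with 95% CIs, robust or bootstrap if residuals are non-normal. Tabulate sport and body composition by arch group, and name the sampling strata. Do not use baseline significance tests to rule out confounding. State that body composition, and possibly sport, may be affected by arch type or affect the footprint index, so the second model may remove part of a real effect. Where the estimates differ, describe the result as an association rather than an influence of foot type. The methods are written in the past tense, so label the models post hoc if the data are already analysed.

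The cost is SAP wording, one table and two models per outcome, with the loss of precision shown above: at f = 0.40, power stays above the planned 0.80 at a VIF of 1.5 but not at 2. Age, weight, height and muscle/fat percentages are already measured. Each athlete's sport is presumably known but is not listed as a recorded variable, so this needs confirming.
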